6.0 TRIAL PROCEDURES

6.1 Trial Procedures

The Trial Flow Chart - Section 5.0 summarizes the trial procedures to be performed at each visit. Individual trial procedures are described in detail below. It may be necessary to perform these procedures at unscheduled time points if deemed clinically necessary by the investigator.

Furthermore, additional evaluations/testing may be deemed necessary by the Sponsor-Investigator and/or Merck for reasons related to subject safety. In some cases, such evaluation/testing may be potentially sensitive in nature (e.g., HIV, Hepatitis C, etc.), and thus local regulations may require that additional informed consent be obtained from the subject. In these cases, such evaluations/testing will be performed in accordance with those regulations.

6.1.1 Administrative Procedures

6.1.1.1 Informed Consent

The Investigator must obtain documented consent from each potential subject prior to participating in a clinical trial.

Consent must be documented by the subject's dated signature or by the subject's legally acceptable representative's dated signature on a consent form along with the dated signature of the person conducting the consent discussion.

A copy of the signed and dated consent form should be given to the subject before participation in the trial.

The initial informed consent form, any subsequent revised written informed consent form and any written information provided to the subject must receive the IRB/ERC's approval/favorable opinion in advance of use. The subject or his/her legally acceptable representative should be informed in a timely manner if new information becomes available that may be relevant to the subject's willingness to continue participation in the trial. The communication of this information will be provided and documented via a revised consent form or addendum to the original consent form that captures the subject's dated signature or by the subject's legally acceptable representative's dated signature.

Specifics about a trial and the trial population will be added to the consent form template at the protocol level.

The informed consent will adhere to IRB/ERC requirements, applicable laws and regulations and Sponsor-Investigator requirements.

6.1.1.2 Inclusion/Exclusion Criteria

All inclusion and exclusion criteria will be reviewed by the investigator or qualified designee to ensure that the subject qualifies for the trial.

6.1.1.3 Medical History

A medical history will be obtained by the investigator or qualified designee. Medical history will include all active conditions, and any condition diagnosed within the prior 10 years that are considered to be clinically significant by the Investigator. Details regarding the disease for which the subject has enrolled in this study will be recorded separately and not listed as medical history.

6.1.1.4 Prior and Concomitant Medications Review

6.1.1.4.1 Prior Medications

The investigator or qualified designee will review prior medication use, including any protocol-specified washout requirement, and record prior medication taken by the subject within 28 days before starting the trial. Treatment for the disease for which the subject has enrolled in this study will be recorded separately and not listed as a prior medication.

6.1.1.4.2 Concomitant Medications

The investigator or qualified designee will record medication, if any, taken by the subject during the trial. All medications related to reportable SAEs and ECIs should be recorded as defined in Section 6.2.

6.1.1.5 Disease Details and Treatments

6.1.1.5.1 Disease Details

The investigator or qualified designee will obtain prior and current details regarding disease status.

6.1.1.5.2 **Prior Treatment Details**

The investigator or qualified designee will review all prior cancer treatments including systemic treatments, radiation and surgeries.

6.1.1.5.3 Subsequent Anti-Cancer Therapy Status

The investigator or qualified designee will review all new anti-neoplastic therapy initiated after the last dose of trial treatment. If a subject initiates a new anti-cancer therapy before the planned Off-Study Visit, that visit may be combined with a standard of care/previously scheduled visit, and tasks related to that visit completed before initiating additional therapy.

6.1.2 Clinical Procedures/Assessments

6.1.2.1 Adverse Event (AE) Monitoring

The investigator or qualified designee will assess each subject to evaluate for potential new or worsening AEs as specified in the Trial Flow Chart (Section 5.0) and more frequently if clinically indicated. Adverse events will be graded and recorded throughout the study and during the follow-up period according to NCI CTCAE Version 4.0 (see Section 12.2). Toxicities will be characterized in terms regarding seriousness, causality, toxicity grading, and action taken with regard to trial treatment. All AEs of unknown etiology associated with MK-3475 exposure should be evaluated to determine if it is possibly an event of clinical interest (ECI) of a potentially immunologic etiology (irAE). Please refer to Section 6.2 for detailed information regarding the assessment and recording of AEs.

6.1.2.2 Physical Exam

The investigator or qualified designee will perform a complete physical exam during the screening period. Clinically significant abnormal findings should be recorded as medical history. A full physical exam should be performed during screening and at EOT. Otherwise, directed physical exams are permissible.

6.1.2.3 Vital Signs

The investigator or qualified designee will take vital signs at screening, prior to the administration of each dose of trial treatment and at treatment discontinuation as specified in the Trial Flow Chart (Section 5.0). Vital signs should include temperature, pulse, respiratory rate, blood pressure. Weight is checked on day 1 of each cycle and at screening. Height will be measured at screening only.

6.1.2.4 Eastern Cooperative Oncology Group (ECOG) Performance Scale

The investigator or qualified designee will assess ECOG status at screening, prior to the administration of each dose of trial treatment and discontinuation of trial treatment as specified in the Trial Flow Chart (Section 5.0).

6.1.2.5 Tumor Imaging and Assessment of Disease

The primary mode of response assessment is contrast-enhanced CT imaging or noncontrast CT or MRI if CT contrast is contraindicated.

For measurement of response based on CT imaging, 2014 criteria will be used as described in "Recommendations for Initial Evaluation, Staging, and Response Assessment of Hodgkin and Non-Hodgkin Lymphoma: The Lugano Classification".²⁸ All CT and scans are to be interpreted locally.

- Baseline imaging must be performed within 8 weeks of initiating study drug therapy. Additional baseline imaging may be performed as indicated for standard of care and clinical purposes including MRI, or CT imaging of the neck. CT neck should be performed for patients with known neck adenopathy.
- Restaging CT will be performed after 8 cycles (week 23-25) then every 3 months thereafter for patients on continued pembrolizumab therapy).
- FDG-PET/CT may be performed as clinically indicated but is not required. In particular, PET/CT is suggested to confirm metabolic CR for patients with residual CT abnormalities of unknown significance, or PR by CT criteria lasting 3 months or more.. A baseline bone marrow aspirate (biopsy optional) is required within 6 months prior to signing consent, if not available. Repeat bone marrow aspirate is required to confirm CR, only for patients with known BM involvement.

6.1.2.6 Tumor Tissue Collection and Correlative Studies Blood Sampling

Assessment of available archival tumor tissue for correlative study analysis will be performed during the screening period. Any available pretreatment biopsy tissue will be provided for central correlative study analysis. In addition, patients will undergo optional lymph node biopsy at baseline and up to one time between cycles 1 and 3, and at the time of persistent or progressive disease. Correlative studies will evaluate the tumor immunomicroenvironment.

Peripheral blood correlative study samples will be performed at the following time-points (see Section 5 Trial Flow Chart):

- 1. Baseline (collected any time prior to cycle 1 day 1 study drug dosing)
- 2. Cycle 5 day 1

3. At the Off-Study assessment visit; or at the time of disease progression, or at time of initiation of second-line therapy (whichever occurs first)

Specimen Requirements: Submission for flow cytometry

- A 5-10 mL specimen of peripheral blood in lavender- (EDTA) or green- (sodium heparin) tube is acceptable for each draw.
- Storage/Transport Temperature: Specimens can be transported with a cold pack or wet ice, but do not fix or freeze specimens.
- Unacceptable Conditions: Frozen specimens, specimens greater than 48 hours old, specimens fixed in formalin for flow cytometry

• Address for shipping blood specimens for flow cytometry: Attn: Hematopathology Lead Seattle Cancer Care Alliance Hematopathology Laboratory G7800 [name]

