3.1.4 Clinical Trial Data

A combination trial of PD1 blockade and rituximab in relapsed or refractory follicular lymphoma has been fully reported. 24 In that study, pidilizumab was tested in combination with rituximab in treating 32 subjects. A median 10 pidilizumab treatments were given, and in conjunction with rituximab produced an overall response rate of 66%; median time to observed response was 88 days (range, 53–392). No deaths were observed for patients on this trial, and no autoimmune or therapy-related grade 3/4 toxicities were seen. It was observed that naïve, effector memory, and central memory CD4+ T cells were increased post-treatment compared to baseline.

An initial clinical trial of anti-PD-1 blockade in DLBCL has been reported, using the monoclonal antibody pidilizumab as maintenance after autologous transplant for relapsed or refractory disease. ²⁵ In that single-arm study, PD1 blockade was safe, with 19% experiencing grade 3-4 neutropenia (without symptoms or complications) the most notable high-grade toxicity; there Protocol v4.0 dated 21 July 2021 Page 10 of 62

was a 3% rate of drug-related SAE's. Notably, 70% of subjects with a positive post-salvage PET CT scan-- typically associated with a poor outcome after transplant35-- remained in remission 16 months after their first dose. Treatment with pidilizumab resulted in a significant increase in the absolute number of PDL1- bearing activated helper T cells in the peripheral blood, and changes in PD-1 bearing monocytes. In addition, an increase in the absolute number of circulating CD8 positive and central memory T cells, as well as CD4 positive central memory T cells, were observed. While exploratory and hypothesis generating, these findings supported an on-target and immunomodulatory effect of anti-PD-1 blockade in the setting of DLBCL.

The Keynote-13 trial, a phase Ib multi-cohort Trial of Pembrolizumab in subjects with hematologic malignancies, includes a cohort with primary mediastinal B-cell lymphoma (PMBCL), a DLBCL variant, with preliminary results presented in abstract form.²⁶ In that study, 19 patients with PMBCL were enrolled and 7/17 with evaluable disease responded. With a median follow-up of 11.3 months, the median duration of response had not been reached, and no patient discontinued therapy due to adverse events. 11 patients experienced treatment-related adverse events, mostly grade 1-2. This trial supports the ongoing study of pembrolizumab for DLBCL and its variants.

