3.1.7.2 Biomarker Research

Tissue-based assays for tumor and immune infiltrate expression of PD1, PD-L1 will be performed by a third party laboratory to be designated by Merck, with tissue received from the most recent biopsy specimen when available.

Patients may undergo an optional tumor biopsy at baseline and up to one time between cycles 1 and 3. Patients may also undergo optional biopsies in the setting of persistent or relapsed disease. Correlative studies will evaluate the tumor microenvironment.

For all patients, baseline and serial evaluation of peripheral blood T cell populations by flow cytometry will be undertaken. In previous studies, alterations of both PD-L1 and PD1 bearing lymphocytes have been observed in peripheral blood. This study will analyze markers including (but not limited to) CD3, CD4, CD8, CD14, PD-1, PD-L1, and PDL-2 on peripheral blood mononuclear cells, and will explore whether alterations in T cell subsets occur with therapy and predict outcomes with treatment.

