4.1.3 Subject Exclusion Criteria

The subject must be excluded from participating in the trial if the subject:

1. Is currently participating and receiving study therapy or has participated in a study of an investigational agent and received study therapy or used an investigational device within 4 weeks of the first dose of treatment.

- 2. Has a diagnosis of immunodeficiency or is receiving systemic steroid therapy or any other form of immunosuppressive therapy within 7 days prior to the first dose of trial treatment, except for physiologic corticosteroid replacement therapy for adrenal or pituitary insufficiency which is permitted.
- 3. Has a known history of active TB (Bacillus Tuberculosis)
- 4. Hypersensitivity to pembrolizumab or any of its excipients.
- 5. Has had a prior anti-cancer monoclonal antibody (mAb) within 4 weeks prior to study Day 1 or who has not recovered (i.e., ≤ Grade 1 or at baseline) from adverse events due to agents administered more than 4 weeks earlier.
- 6. Prior allogeneic transplant, within the last 5 years.
- 7. Has had prior chemotherapy, targeted small molecule therapy, or radiation therapy within 2 weeks prior to study Day 1 or who has not recovered (i.e., ≤ Grade 1 or at baseline) from adverse events due to a previously administered agent.
 - Note: Subjects with \leq Grade 2 neuropathy are an exception to this criterion and may qualify for the study.
 - Note: If subject received major surgery, they must have recovered adequately from the toxicity and/or complications from the intervention prior to starting therapy.
- 8. Has a known additional malignancy that is progressing or requires active treatment. Exceptions include basal cell carcinoma of the skin or squamous cell carcinoma of the skin that has undergone potentially curative therapy or in situ cervical cancer.
- 9. Has known active central nervous system (CNS) metastases and/or lymphomatous meningitis. Subjects with previously treated brain metastases or lymphomatous meningitis may participate provided they are stable (without evidence of progression by imaging for at least four weeks prior to the first dose of trial treatment and any neurologic symptoms have returned to baseline), have no evidence of new or enlarging brain metastases, and are not using steroids for at least 7 days prior to trial treatment.

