2. See Section 6.1.2.5: Baseline CT imaging must be performed within 8 weeks of initiating study drug therapy. CT neck should be included for patients with palpable or known neck adenopathy. End of induction CT will be done before cycle 5 (week 11-13 of therapy). For patients on continued therapy, restaging CT will be performed before cycle 9 (week 23-25) and then every 3 months thereafter. Other imaging may be performed at clinician's discretion, including FDG PET/CT and/or MRI.								
3. The presence of archival tissue will be assessed during screening. When available this tissue will be provided for central biomarker analysis including PD1/PDL1 expression on tumor cells. Patients may undergo optional lymph node biopsy at baseline and up to one time between cycles 1 and 3. Patients may also undergo optional biopsies in the setting of persistent or progressive disease, and tissue may be provided for correlative analysis at that time.								
4. See section 6.1.2.6 for details on correlative study draws, which are drawn at baseline (any time prior to cycle 1 day 1 study drug dosing), cycle 5 day 1, and at the Off-Study visit (or at the time of disease progression/initiation of second-line therapy whichever occurs first).								

5. Bone marrow aspirate (biopsy is not mandatory but is permitted) for routine analysis for lymphoma involvement will be performed at baseline for patients who have not undergone a marrow within 6 months prior to signing consent, and again to confirm complete response.

6. Negative Urine or serum pregnancy test is required within 72 hours prior to receiving the first dose of study medication.

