6.1.4.1 Screening

6.1.4.1.1 Screening Period

The screening period begins upon signing consent and includes evaluation of available tissue specimen for study-related, central review, any ancillary/staging/laboratory testing or other evaluations prior to Cycle 1 Day 1 of study therapy. The screening period may last up to 42 days (6 weeks).

Laboratory studies collected within the 42 days prior to study drug start, for standard of care purposes, may be used to satisfy screening requirements and do not need to be repeated at screening. In addition, if lab studies are done within 7 days of cycle 1 day 1, they do not need to be repeated for study purposes. Archival bone marrow aspirate /biopsy data is acceptable if performed within the 6 months prior to signing consent.

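### The baseline flow-cytometry sample may be drawn before the prior-therapy washouts have run, so T-cell changes to cycle 5 can mix recovery with study-drug effect in patients sampled early

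*Combined protocol and SAP*

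**What the plan says.** **Sample timing.** Section 6.1.2.6 lists the first correlative blood sample as "Baseline (collected any time prior to cycle 1 day 1 study drug dosing". Footnote 4 of the flow chart (5.1) repeats the rule: samples are "drawn at baseline (any time prior to cycle 1 day 1 study drug dosing), cycle 5 day 1, and at the Off-Study visit", the last of these moving to progression or second-line therapy if that comes first. The flow chart marks the baseline sample in the screening column (days -42 to -1), not at cycle 1 day 1.

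**Screening.** Under 6.1.4.1.1, "The screening period begins upon signing consent" and "The screening period may last up to 42 days (6 weeks").

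**Washouts.** All are counted back from treatment start. In 4.1.3, steroids and other immunosuppressants are excluded "within 7 days prior to the first dose of trial treatment". Chemotherapy, targeted small molecules and radiation are excluded within 2 weeks of Day 1. For antibodies the criterion reads "Has had a prior anti-cancer monoclonal antibody (mAb) within 4 weeks prior to study Day 1".

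**Ban during screening.** Section 4.3.2 prohibits antineoplastic chemotherapy and biological therapy, radiation and most systemic glucocorticoids in the screening and treatment phases, with some exceptions.

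**Use of the sample.** Section 3.1.7.2 states: "For all patients, baseline and serial evaluation of peripheral blood T cell populations by flow cytometry will be undertaken". It will explore whether T-cell subsets shift on treatment and whether such shifts predict outcome. Section 7.0 offers t-tests and regression for the correlative data, both optional, and names no covariates.

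**The concern.** The protocol protects the first dose from recent immunosuppressive or cytotoxic therapy but does not protect the blood sample that serves as the reference for immune change. The cells being counted are lymphocytes, and 4.1.3 itself groups systemic steroids with immunosuppressive therapy. If a patient is sampled soon after such therapy, some of the difference between that sample and cycle 5 day 1 may be recovery that would have occurred without pembrolizumab or the CD20 antibody. Each arm is uncontrolled, so recovery cannot be subtracted, and the plan carries no term for time since prior therapy or for day of draw.

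At stake is exploratory objective 1, correlates of response by peripheral blood flow cytometry. A poorly timed baseline cannot be redrawn once dosing has begun.

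**Working it through.** The plan states no sample size, power or error rate for the correlative study, so there is no figure to reproduce. The check is calendar arithmetic plus one illustration.

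**Inputs**
- Screening up to 42 days (6.1.4.1.1; flow chart).
- Washouts W = 7, 14 and 28 days before first dose or Day 1 (4.1.3).
- Induction of four 3-week cycles (6.1.5).
- Arm sizes up to 20, 17 and 25 (Trial Summary).

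**1. Exclusion criteria alone.** The part of the window in which a washout need not yet be complete is 42 - W days:
- steroids and immunosuppressants: 42 - 7 = 35 of 42 (83%)
- chemotherapy, small molecules, radiation: 42 - 14 = 28 of 42 (67%)
- antibodies: 42 - 28 = 14 of 42 (33%)

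These are upper limits because they ignore 4.3.2.

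**2. Adding the ban in 4.3.2.** Let g be the days from last therapy to consent, s the days from consent to the draw, and L the days from consent to first dose. Then
- gap at first dose = g + L, which 4.1.3 requires to be at least W
- gap at the draw = g + s, which no section constrains

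With g = 1, s = 0 and L = 42, the gap at first dose is 43 days, so all three washouts are met, while the gap at the draw is 1 day. If the ban is followed, a draw at s of W or more is safe whatever g is. The exposed draws are therefore those in the first 7, 14 or 28 days after consent, and only in patients with g < W - s. The ban narrows the gap but does not close it.

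**3. Interval to the next sample.** Cycle 1 day 1 to cycle 5 day 1 is 4 x 21 = 84 days. A baseline drawn up to 42 days earlier gives up to 84 + 42 = 126 days, a ratio of 126/84 = 1.5. Visit windows and dosing delays are ignored.

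**4. Illustration of possible size.** Assume no drug effect, and that a fraction f of patients carries a recovery shift of d standard deviations of the change, all in one direction. The mean bias is f x d. A one-sample t-test on the change (two-sided 5%, 40,000 simulated trials) rejects as follows:

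| f | d | bias (SD) | n = 17 | n = 20 | n = 25 |
|---|---|---|---|---|---|
| 0.25 | 0.5 | 0.125 | 7.6% | 7.9% | 9.0% |
| 0.25 | 1.0 | 0.25 | 14.2% | 15.7% | 19.3% |
| 0.50 | 0.5 | 0.25 | 15.4% | 17.7% | 22.0% |
| 0.50 | 1.0 | 0.50 | 40.8% | 47.1% | 57.4% |

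With f = 0 the rate is about 5%. Both f and d are assumptions, and neither is in the documents.

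**5. After the change.** With a pre-dose draw on cycle 1 day 1, s = L. The gap at the draw then equals the gap at first dose (at least 7, 14 or 28 days), and the interval to cycle 5 day 1 is about 84 days for everyone.

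**The case against.** The strongest reply is 4.3.2. Most of the relevant therapies are barred from consent, so a contaminated baseline needs a patient who stopped treatment shortly before consent and was also sampled early. That is right, and it limits how many patients are affected. It does not remove the problem, because nothing discourages that combination. (Sections 4.1.3 and 4.3.2 also imply different limits within screening and should be reconciled. The point stands whichever governs.)

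A second reply is that the data for adjustment already exist: prior cancer treatments are reviewed (6.1.1.5.2), recent medications are recorded (4.3.1, 6.1.1.4.1), and 7.0 allows regression. This stands in part. No adjustment is planned, however, and 4.3.1 reaches back only 28 days from first dose. A steroid given for another condition and stopped on day -43, one day before a day -42 draw, falls outside that record.

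A third reply is that a flexible window guards against missing baselines in arms of 17 to 25, given that specimens may not be frozen or exceed 48 hours. This is a fair cost. The cycle 5 day 1 sample already works under the same handling limits.

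Several stronger readings are tempting but not supported:
- **Absolute T-cell counts cannot be derived at baseline.** The cited pidilizumab study did report "an increase in the absolute number of circulating CD8 positive and central memory T cells", and nothing pairs the baseline blood count with the flow tube. But absolute counts are not a planned variable here, the flow chart schedules a blood count in screening, and the third sample may also lack a same-visit count if it is taken at progression or second-line therapy.
- **The error is tied to outcome because aggressive disease means more recent therapy.** No section says so.
- **Most baselines are affected.** The 83%, 67% and 33% are shares of window days under 4.1.3 alone, not shares of patients.

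**Conclusion.** The gap is real and minor. The timing rule permits a baseline that may precede completion of the washouts, by enough in the extreme case to leave about 1 day since last therapy instead of the 7, 14 or 28 assured at first dose. It also lets the baseline-to-cycle-5 interval range from about 84 to 126 days. In patients sampled early after recent therapy, recovery and study-drug effect can be mixed.

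Three assumptions underlie this. The comparison of interest is taken to be change from baseline, which is inferred from 3.1.7.2 and 7.0 because no such variable is formally defined. Recent therapy is taken to shift the measured subsets, by an amount the documents do not give. Some patients are assumed to be drawn early, in unknown number. The rejection rates above show what could happen under stated assumptions and are not estimates for this trial.

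A reader might infer that the efficacy results are compromised. They are not: response rate, PFS, OS, safety and the two-stage rules do not use this sample.

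**What to change.** In 6.1.2.6 and flow-chart footnote 4, replace the present baseline timing with: *on cycle 1 day 1, before premedication and study drug*. Move the flow-chart mark to that column.

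Where a cycle 1 day 1 draw is not feasible, allow one planned in advance for the last few days before cycle 1 day 1, once the 4.1.3 washout intervals have elapsed. It has to be arranged beforehand, because a missed pre-dose sample cannot be recovered after dosing.

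Record the draw date and the last dates of prior steroid, chemotherapy, radiation and antibody therapy, reaching back far enough to cover the draw. In 7.0, name time since last therapy as a covariate, or as a restriction in a sensitivity analysis.

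A blood count with differential at the same draw is optional, and needed only if absolute subset counts will be reported.

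The cost is a wording change and a few date fields. Every treated patient attends cycle 1 day 1, so the number of flow tubes does not rise. The price is slightly less scheduling flexibility and a small risk of a missed baseline. Recovery that continues after Day 1 would still fall within the 84 days to cycle 5, so the confounding is reduced and not removed.
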